#### **7.1.3.1 Subjects Randomized to EVICEL®**

For subjects randomized to receive EVICEL® Fibrin Sealant (Human), a thin layer will be applied to cover the entire length of the suture line and the adjacent, including all suture holes. If necessary, a second layer of EVICEL® may be applied. A cure time of 1-2 minutes should be allotted between layers to allow for clot formation and stabilization. CSF leakage will be evaluated with the Valsalva maneuver performed to an intra-thoracic pressure between 20-25 cm H2O for 5-10 sec.

If a CSF leakage is still apparent a second treatment (up to two layers) with EVICEL® may be applied. CSF leakage will be re-evaluated with the Valsalva maneuver as described above. If watertight closure is achieved for EVICEL® treatment, no further treatment, including the use of onlays, will be allowed.

If watertight closure is not evident after the final Valsalva maneuver, the subject will be deemed a failure and surgeon may revert to his/her standard of care for closure, this can include additional treatment with EVICEL® if clinically appropriate. The use of other fibrin sealants is not permitted.

Subjects randomized to EVICEL® may not have their dura treated with DuraSeal™ Dural Sealant System or any other PEG based or fibrin sealants.

Closure of the remaining layers of the surgical site will be performed according to the surgeon's standard practice.

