#### **7.1.3.2 Subjects Randomized to DuraSeal™**

For subjects randomized to DuraSeal™, the assigned product will be applied to the entire length of the suture line, including all suture holes, according to the manufacturer's instruction for use. CSF leakage will

be evaluated with the Valsalva maneuver performed to an intra-thoracic pressure between 20-25 cm H2O for 5-10 seconds.

If a CSF leakage is still apparent, continue treatment with Duraseal™ per manufactures directions. CSF leakage will be re-evaluated with the Valsalva maneuver as described above. If watertight closure is achieved for DuraSeal™ treatment, no further treatment, including the use of onlays, will be allowed.

If watertight closure is not evident after the final Valsalva maneuver, the subject will be deemed a failure and surgeon may revert to his/her standard of care for closure, this can include additional treatment with DuraSeal™, if clinically appropriate. The use of fibrin sealants is not permitted.

Subjects randomized to DuraSeal™ may not have their dura treated with EVICEL® Fibrin Sealant or any other PEG based or fibrin sealants.

Closure of the remaining layers of the surgical site will be performed according to the surgeon's standard practice.

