## 8.3 Effectiveness

### 8.3.1 Effectiveness Variables

The primary endpoint is the proportion of subjects that do not have a CSF leak during surgery and up to the 30-day (-/+7) post-operative period. A subject is declared as a success when the following conditions are met:

- absence of intra-operative CSF leak following Valsalva maneuver, and
- absence of CSF leak or pseudomeningocele in the surgical area during the 30-day follow-up period.

The primary effectiveness parameter will be analyzed using the ITT and Per-Protocol analysis sets. The Per-Protocol analysis will be considered primary effectiveness analysis.

There are no secondary effectiveness endpoints for this study.

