3. STUDY ENDPOINTS

The primary endpoint is the proportion of subjects that do not have a CSF leak during surgery and up to the 30-day (-/+ 7) post-operative period. A subject is declared as a success when the following conditions are met:

- absence of intra-operative CSF leak following final Valsalva maneuver, and
- absence of CSF leak or pseudomeningocele in the surgical area during the 30-day (-/+ 7) follow-up period.

A confirmed CSF leak or pseudomeningocele is diagnosed by physical examination, diagnostic testing, imaging study or the need for surgical intervention to directly treat a CSF leak during the 30-day (-/+ 7 days) follow-up at the location where randomized treatment was applied.

In addition, the following safety endpoints will be included in this study:

- Incidence of intra-operative CSF leakage following final Valsalva maneuver;
- Incidence of post-operative CSF leakage within 30 days (± 7) post-operatively;
- Incidence of post-operative CSF leakage within 60 (± 14) days post-operatively;
- Incidence of surgical site infections (SSI) according to NNIS definition and CDC classification within 30 days (± 7) post-operatively;
- Incidence of adverse events, collected from time of randomization, throughout the follow-up period until 60 days (± 14) after the procedure.

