7. PROCEDURE DATA

Procedure data will be summarized descriptively for subjects in each treatment group in the ITT set to assess comparability of treatment groups. The categorical data will be summarized descriptively by frequencies along with the associated percentages. The continuous data will be presented using summary statistics such as number of subjects, mean, standard deviation, minimum, median and maximum.

The following procedure variables will be analyzed:

- Operative procedure, including type of approach, indication for surgery and tumor type and location, if applicable;
- Operating room (OR) time;
- Procedure duration (from first incision to closure completion);

- CSF leak determination;
- Specification of treatment to which subject is randomized;
- For patients treated with EVICEL, the following data will be analyzed for first EVICEL application and second treatment of EVICEL (if applicable): method of EVICEL application, number of layers applied, indication of spontaneous leak observation, indication of Valsalva maneuver performed after randomized treatment application (if applicable), indication of CSF leak detection after Valsalva (if applicable) and definition of leak (if applicable);
- For patients treated with Control (DuraSeal), the following data will be analyzed for first DuraSeal application and second treatment of DuraSeal (if applicable): method of DuraSeal application, number of layers applied, indication of spontaneous leak observation, indication of Valsalva maneuver performed after randomized treatment application (if applicable), indication of CSF leak detection after Valsalva (if applicable) and definition of leak (if applicable);
- Total number of kits used, approximate total amount of randomized treatment used, and derived volume per kit;
- Indication of watertight closure after randomized treatment application;
- Indication of additional treatment application;
- Indication of watertight closure at the end of procedure;
- Indication and specification of additional treatments/rescue therapy applied, such as glues/sealants, sutures, hemostasis matrices, autologous and biologic/non-autologous dural patches.

In addition, the following post-procedure to hospital discharge data will be summarized:

- CSF leak and/or pseudomeningocele determination, along with the identification of the test used for diagnosis;

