8.2 Primary effectiveness analysis

The primary endpoint is the proportion of subjects that do not have CSF leak during surgery and up to the 30-day (± 7) post-operative period. A subject is declared success when the following conditions are met:

- Absence of intra-operative CSF leak following Valsalva maneuver, and
- Absence of CSF leak or pseudomeningocele in surgical area during the 30-day follow-up period.

The primary effectiveness parameter will be analyzed using the ITT and Per-Protocol analysis sets. The Per-Protocol analysis will be the primary effectiveness analysis.

The analysis for the ITT set will be performed considering missing data as failures; in addition, sensitivity analyses for the ITT set will be performed considering missing data as successes, and, as worst-case, with missing data for the EVICEL[®] group considered as failures and missing data for the DuraSeal[™] group considered as successes.

The statistical hypothesis for testing the treatment difference is presented as follows:

- $H_0: \Delta \leq -0.10$ tested against the alternative hypothesis
- $H_a: \Delta > -0.10$.

where:

- Δ is the difference between the success rates of Experimental and Control (Experimental minus Control)
- -0.10 is the non-inferiority difference
- The assumed proportion of successes for Control is 0.95.

P_C is the proportion of success in DuraSeal[™] Control subjects and P_E is the proportion of success in EVICEL[®] subjects.

Two hundred and two (202) evaluable subjects (101 per arm) will achieve 90% power to detect a non-inferiority margin difference in group proportions of -0.10. The proportion of successes in the Control group is 0.95. The proportion of successes in EVICEL[®] group is assumed to be 0.85 under the null hypothesis of inferiority. The power was computed for the case when the actual proportion of successes in the EVICEL[®] group is 0.95. The one-sided significance level of the test is 0.025.

If the lower limit of the one-sided 97.5% confidence interval for Δ is greater than -0.10, then it will be concluded that EVICEL[®] is considered to be non-inferior to DuraSeal[™].

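### Do the shorter success criteria in SAP 8.2 and Protocol 8.3.1 create a second definition of the primary endpoint?

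*SAP*

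**What the plan says.** The primary endpoint is stated five times. The Synopsis, Protocol 2 and SAP 3 give the full form. In SAP 3 the intra-operative condition reads "absence of intra-operative CSF leak following final Valsalva maneuver, and", and the post-operative condition carries the 30-day (-/+7) window.

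Protocol 8.3.1 and SAP 8.2 give a shorter form. The Protocol has "absence of intra-operative CSF leak following Valsalva maneuver, and" and the SAP has "Absence of intra-operative CSF leak following Valsalva maneuver, and". The post-operative bullet in SAP 8.2 is "Absence of CSF leak or pseudomeningocele in surgical area during the 30-day follow-up period", with no tolerance on the 30 days; the bullet in Protocol 8.3.1 is equivalent. However, the sentence that opens the endpoint definition in SAP 8.2 describes subjects who "do not have CSF leak during surgery and up to the 30-day (± 7) post-operative period", and Protocol 8.3.1 opens in the same way.

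More than one post-treatment test is possible. For EVICEL, Protocol 7.1.3.1 says "If a CSF leakage is still apparent a second treatment (up to two layers) with EVICEL® may be applied". For DuraSeal, Protocol 7.1.3.2 says "If a CSF leakage is still apparent, continue treatment with Duraseal™ per manufactures directions". Each is followed by a repeat Valsalva. SAP 7 and the operative tables in SAP 10.2.2 record leak results separately for a first and a second treatment in both arms.

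**The concern.** SAP 8.2 is headed as the primary effectiveness analysis, so its wording carries weight. The dataset will hold up to two post-treatment Valsalva results per patient, and an unqualified reference to Valsalva does not say which one counts. A patient who leaks at the first test and is sealed at the second is a success under SAP 3. If the SAP 8.2 bullet is read as the first test, the same patient is a failure. Read alone, the second bullet would also ignore a leak on days 31 to 37.

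The DuraSeal text adds a further worry. It gives no number of re-treatments, whereas the EVICEL text describes one second treatment. If *final* came after more attempts in one arm than in the other, the comparison could be tilted, in a trial where the surgeon knows the product. With success near 95% and about 100 patients per arm, a few reclassified patients can decide non-inferiority.

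**Working it through.** **The plan's own figure.** Inputs from SAP 8.2: success 0.95 in both arms, margin 0.10, one-sided alpha 0.025, power 90%, 101 per arm.

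- n per arm = (1.960 + 1.282)² × (0.95×0.05 + 0.95×0.05) / 0.10² = 10.51 × 0.095 / 0.01 = 99.8, so 100 against 101 stated.
- Power at 101 = Φ(0.10 / √(0.095/101) − 1.960) = Φ(3.261 − 1.960) = 0.903. Exact enumeration of the Wald test also gives 0.903.

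The design figure is reproduced, and it does not depend on which wording of the bullets is used.

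**The texts side by side.**

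| Place | Valsalva that counts | Window |
|---|---|---|
| Synopsis, Protocol 2, SAP 3 | final | 30 days ±7 |
| Protocol 8.3.1, SAP 8.2: opening sentence | not specified | 30 days ±7 |
| Protocol 8.3.1, SAP 8.2: bullets | unqualified | 30 days, no tolerance |
| Protocol 7.1.3.1 and 7.1.3.2: failure rule | final, both arms | not applicable |
| Intra-operative leak endpoint (Protocol 8.4.1, SAP 3, SAP 9.1) | final | not applicable |

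No row names the first test or any test. The any-test reading also defeats itself. A leak at primary closure, either spontaneous or on the baseline Valsalva, is required for entry (Protocol 4.2), so every patient who entered on a baseline-Valsalva leak would be a failure before treatment. The bullet needs a qualifier, and *final* is the only one the documents supply.

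**The window.** The opening sentence of each section carries the ±7 days, and Protocol 7.1.5 gives the visit the same tolerance. Days 31 to 37 drop out only if a bullet is separated from its own paragraph.

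**Size if the wrong reading were used.** The documents give no share of patients sealed only on re-treatment. Assume it removes 5 or 10 points of success from both arms (Wald, 101 per arm):

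- 0.90 in both arms: Φ(0.10 / √(0.18/101) − 1.960) = Φ(0.409) = 0.659; exact 0.665.
- 0.85 in both arms: Φ(0.10 / √(0.255/101) − 1.960) = Φ(0.030) = 0.512; exact 0.515.
- 0.93 for EVICEL only: Φ(0.08 / √((0.0475 + 0.0651)/101) − 1.960) = Φ(0.436) = 0.669; exact 0.685.

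**How many patients matter.** Start from 5 failures in each arm of 101 and reclassify EVICEL patients only.

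- 8 against 5: difference −3/101 = −0.0297; standard error √((93×8 + 96×5)/101³) = 0.0345; lower limit −0.0297 − 1.960×0.0345 = −0.097. Non-inferiority still holds by Wald.
- 9 against 5: difference −0.0396; standard error √((92×9 + 96×5)/101³) = 0.0356; lower limit −0.109. It fails.

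Reversal therefore needs 4 reclassified EVICEL patients by Wald. By the Miettinen-Nurminen score method, which tolerates 7 failures against 5, it needs 3. Both counts assume that no DuraSeal patient is reclassified.

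**The case for a change.** The best case for a change is that the primary-analysis section should stand on its own. A statistician should not need four other places to learn which of two recorded results defines success, and a choice between readings made after unblinding would look driven by the result. SAP 4 declares no changes to the planned analysis, so nobody intended a new definition, and aligning the bullets would cost almost nothing. That is fair as a comment on drafting. It does not show that the plan lacks a rule: SAP 3 is the endpoint section of the same document, and a programmer would have to ignore it to go wrong.

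The results-table titles in SAP 10.2.2 use a third form, running to the 30-day visit. That visit has the ±7-day tolerance, so the titles are shorthand. The exact cut-off for a patient seen early in the window is a detail for the derivation; the sections do not conflict on it.

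The point about unequal attempts is partly right. Protocol 6.2 and 7.1.3.2 and SAP 7 describe DuraSeal re-treatment in different terms, and those passages should be reconciled when the text is next edited; no position is taken here on how many treatments are right. An actual imbalance cannot be shown from the documents, because the DuraSeal text defers to manufacturer's instructions that are not included. What is visible is parallel: a repeat Valsalva after re-treatment, the same failure rule, and first and second treatments tabulated for both products.

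**Conclusion.** The omission is real but clerical. Read as a whole, the plan has one definition: success requires no leak at the final Valsalva, and no leak or pseudomeningocele through the 30-day (±7) follow-up. A sponsor following both documents would score it that way. Aligning the bullets would then change no patient's outcome and leave the 202 evaluable subjects and 90.3% power as they are.

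The drop to about 66% or 51% requires both a misreading that SAP 3 and the surgical procedures rule out and an assumed loss of 5 or 10 points in each arm. The reversal by 3 or 4 patients requires the same misreading, acting on EVICEL patients alone. The conclusion assumes that the endpoint is derived from the full SAP and not from one bullet taken in isolation.

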**STATISTICAL DESIGN:**

This is a non-inferiority trial using a one-sided alpha 0.025 and 90% power. The assumed success rate in the both arms is 95%.

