5. ANALYSIS SETS

The following three analysis sets defined:

- Intent-to-treat (ITT) set consists of all enrolled and randomized subjects.
- Per-Protocol (PP) set consists of all ITT subjects who have data available for primary effectiveness endpoint and have no major protocol deviations.
- Safety set consists of all enrolled subjects who receive a study treatment.

The primary endpoint will be analyzed using the ITT and the PP set. However, the primary analysis will be based on the PP set. The ITT analysis will be considered confirmatory.

Major protocol deviations are deviations that have an impact on the primary endpoint, or that have an impact on the randomization assignment. These will be determined prior to database lock.

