For the primary endpoint, the comparability between the surgical procedure (posterior fossa or supratentorial approach) subgroups will be evaluated using a logistic regression analysis, with success/failure for primary endpoint as dependent variable and with surgical procedure, treatment group, and interaction between surgical procedure and treatment group as independent variables included in the model. The interaction terms will be considered significant at 0.15 significance level in the logistic regression model. The effect of select demographics and baseline characteristics on the primary endpoint may also be evaluated. In addition, the primary endpoint will be compared between treatment groups using a Cochran-Mantel-Haenszel (CMH) Chi-square test adjusting for the surgical procedure at 0.05 significance level.

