APPENDIX 1: TABLE TEMPLATES (SEE ATTACHED DOCUMENT)

APPENDIX 2: CDC/NHSN CRITERIA FOR DEFINING A SURGICAL SITE INFECTION (SSI)

Superficial Incisional SSI

Infections occur within 30 days after the operation *and* infection involves only skin or subcutaneous tissue of the incision *and* at least *one* of the following:

1. Purulent drainage, with or without laboratory confirmation, from the superficial incision.
2. Organisms isolated from an aseptically obtained culture or fluid or tissue from the superficial incision.
3. At least one of the following signs or symptoms of infection: pain or tenderness, localized swelling, redness, or heat *and* superficial incision is deliberately open by surgeon, *unless* incision is culture-negative.
4. Diagnosis of superficial incisional SSI by the surgeon or attending physician.

Do *not* report the following conditions as SSI:

1. Stitch abscess (minimal inflammation and discharge confined to the points of suture penetration).
2. Infection of an episiotomy or newborn circumcision site.
3. Infected burn wound.
4. Incisional SSI that extends into the fascial and muscle layers (see deep incisional SSI).

Note: Specific criteria are used for identifying infected episiotomy and circumcision site and burn wounds.

Deep Incisional SSI

Infections occurs within 30 days after the operation if no implant is left in place or within 1 year if implant is in place and the infection appears to be related to the operation *and* infection involves deep soft tissues (e.g., fascial and muscles layers) of the incision *and* at least *one* of the following:

1. Purulent drainage from the deep incision but not from the organ/space component of the surgical site.
2. A deep incision spontaneously dehisces or is deliberately opened by a surgeon when the patient has at least one of the following signs or symptoms: fever ($>38^{\circ}\text{C}$), localized pain, or tenderness, unless site is culture-negative.
3. An abscess or other evidence of infection involving the deep incision is found on direct examination, during reoperation, or by histopathologic or radiologic examination.
4. Diagnosis of a deep incisional SSI by a surgeon or attending physician.

Notes:

1. Report infection that involves both superficial and deep incisional sites as deep incisional SSI.
2. Report organ/space SSI that drains through the incision as a deep incisional SSI.

Organ/space SSI

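### The supplied text names no confidence interval method for the only non-inferiority rule, and none of six common intervals gives both the stated 90% power and 2.5% error at 101 per arm

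*SAP*

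**What the plan says.** SAP 8.2 gives the decision rule, which begins "If the lower limit of the one-sided 97.5% confidence interval for"; non-inferiority is concluded when that limit for the difference (EVICEL minus DuraSeal) is above -0.10. The Protocol synopsis, 8.1 and 8.3.2 give the same rule. None of these places says how the limit is calculated.

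The operating characteristics are stated flatly. SAP 8.2 has "Two hundred and two (202) evaluable subjects (101 per arm) will achieve 90% power" and "The one-sided significance level of the test is 0.025". It takes 0.95 as the control rate and says that the EVICEL "group is assumed to be 0.85 under the null hypothesis of inferiority"; power is for 0.95 in both arms. The Protocol synopsis repeats the design: "This is a non-inferiority trial using a one-sided alpha 0.025 and 90% power".

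SAP 5 sets the analysis population: "However, the primary analysis will be based on the PP set".

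On surgical approach, Protocol 8.2.1 makes it a stratification factor for the overall analysis without tying it to the interval. SAP 8.2 names two approach-adjusted analyses: a logistic model with an interaction term, and a second in which the endpoint is "compared between treatment groups using a Cochran-Mantel-Haenszel (CMH) Chi-square test adjusting for the surgical procedure at 0.05 significance level".

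The list of tables in SAP 10.2.2 describes the primary table (14.2.1.1) only as discrete data using shell G2. The shells are a separate attachment: "APPENDIX 1: TABLE TEMPLATES (SEE ATTACHED DOCUMENT)".

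**The concern.** With success rates near 95% and about 100 subjects per arm, the usual intervals for a difference of proportions disagree by enough to matter against a margin of -0.10. The two approach-adjusted analyses that the SAP does name do not fill the gap, because neither gives a confidence limit for the difference or tests it against the margin.

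Two things are at stake. First, the same data can pass or fail depending on an unstated choice, and this limit is the trial's only confirmatory decision. Second, the stated 90% power and 0.025 level may not be available together. If the interval that delivers the power has an error above 0.025, the excess favours declaring non-inferiority.

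**Working it through.** **Inputs.** From SAP 8.2: margin -0.10; one-sided level 0.025; 101 evaluable subjects per arm; 0.95 in both arms for power; 0.85 against 0.95 at the null. From Protocol 8.1: about 230 enrolled, so 115 per arm if none is lost. z(0.975) = 1.95996 and z(0.90) = 1.28155.

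**Step 1: reproduce the plan's figure.** With the unpooled normal approximation,

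n per arm = (1.95996 + 1.28155)² × 2 × 0.95 × 0.05 / 0.10² = 10.507 × 9.5 = 99.8.

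This rounds up to 100, against 101 in the plan. Exact Wald power is 88.6% at 100 per arm and 90.3% at 101. The stated size and power are consistent with a Wald limit.

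**Step 2: exact power and error.** For each interval, every pair of success counts at 101 per arm was enumerated, the rule (lower limit above -0.10) was applied, and the binomial probabilities of the passing pairs were summed.

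| Interval | Power at 0.95/0.95 | Error at 0.85/0.95 |
|---|---|---|
| Wald, unpooled | 90.3% | 3.3% |
| Agresti-Caffo | 88.3% | 2.9% |
| Hauck-Anderson | 87.1% | 2.6% |
| Continuity-corrected Wald | 83.4% | 1.9% |
| Newcombe | 83.3% | 2.5% |
| Miettinen-Nurminen | 82.9% | 2.2% |

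None has power of at least 90% and error of at most 2.5%. The Wald error depends on the control rate: 2.7% at 0.90, 3.3% at 0.95, 4.1% at 0.97 and 4.7% at 0.98.

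**Step 3: unequal arms.** Over all splits of 202 from 96/106 to 106/96, Wald has 88.4% to 90.3% power and 3.0% to 3.4% error. Miettinen-Nurminen has 81.1% to 84.2% power and 2.0% to 2.4% error.

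**Step 4: can the choice change the verdict?** Take 93/101 EVICEL and 96/101 DuraSeal successes. The difference is -3/101 = -0.0297. For Wald,

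SE = √(0.9208 × 0.0792/101 + 0.9505 × 0.0495/101) = 0.0345,

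and the limit is -0.0297 - 1.960 × 0.0345 = -0.0973, a pass. The other limits are Agresti-Caffo -0.09998 (pass), Hauck-Anderson -0.1025, Newcombe -0.1046, Miettinen-Nurminen -0.1060 and continuity-corrected Wald -0.1072 (all fail).

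At 101 and at 115 per arm, every result that passes by Miettinen-Nurminen also passes by Wald, so the discordance at 0.95/0.95 is the difference in power:

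- 101 per arm: 0.9033 - 0.8294 = 0.0739, or 7.4% of trials (5.2% to 8.1% over the splits in step 3);
- 115 per arm: 0.9275 - 0.8802 = 0.0473, or 4.7%.

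**Step 5: full enrolment.** At 115 per arm, power and error are Wald 92.8% and 3.1% (0.0305), Hauck-Anderson 90.4% and 2.4%, Newcombe 88.0% and 2.45%, and Miettinen-Nurminen 88.0% and 2.35%.

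**Step 6: stratification.** The documents give no stratum success rates, so these are assumptions. Simulation with Mantel-Haenszel weights (400,000 trials per case) gave the following at 101 per arm. With 30 posterior fossa and 71 supratentorial subjects per arm and a common rate of 0.95: Wald 90.4% and 3.3%, Miettinen-Nurminen 83.0% and 2.2%. With 40 and 61 subjects and rates of 0.90 and 0.983: Wald 91.1% and 3.3%, Miettinen-Nurminen 82.1% and 2.2%. Stratifying does not remove the gap.

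**The case against.** **The power statement is not a miscalculation.** A reader might infer that 90% is wrong, or that the trial really has 83% power. The documents do not support that. The figure is correct for a Wald-type limit, and 83% applies only if a score interval is adopted. What remains is that a sample-size formula does not specify an analysis, and that under Wald the stated 0.025 is a nominal level, which the plan does not say.

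**Every such interval is approximate, including the one preferred here.** This is fair. A reader might infer that Miettinen-Nurminen holds 2.5% everywhere. It does not: at 101 per arm its exact error is 2.55% at a control rate of 0.80 and peaks at about 2.75% near 0.55. Near the design rates it is at or below 2.5% (2.2% at 0.95), where Wald is about one third over.

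**Thresholds are sensitive to discreteness.** This stands in part. Wald itself reaches 90% at only two of the eleven splits in step 3 (101/101 and 105/97), so the exact 90% line should not be pressed. The Wald error of 3.0% to 3.4% is stable.

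**Full enrolment helps.** With all 230 evaluable, Hauck-Anderson does meet both figures at the plan's null, although its error is 2.7% at a control rate of 0.97 and 3.0% at 0.98. That case needs no losses, whereas SAP 5 removes subjects with missing primary data or major deviations from the primary set.

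**The 7.4% is close to the largest contrast among the six.** Wald against Agresti-Caffo is 2.0%, and Hauck-Anderson against Miettinen-Nurminen is 4.1%. The 93 against 96 example is a boundary case.

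**The approach-adjusted analyses may satisfy Protocol 8.2.1.** That is a possible reading, so no contradiction with the SAP is claimed. It still leaves open whether the deciding interval is stratified.

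**The method may be in the table shells.** This cannot be excluded, since they were not supplied.

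**Conclusion.** The point holds for the supplied text. The sole non-inferiority rule lacks an interval method and a statement on stratification. The plan also gives a power and a one-sided level that none of the six intervals checked delivers together at 101 per arm. The natural reading, Wald, has 90.3% power but about 3.3% exact error at the plan's own null, on the side that favours declaring non-inferiority. The choice between Wald and Miettinen-Nurminen would alter the verdict in 7.4% of trials at 101 per arm and 4.7% at 115.

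These figures rest on the plan's design rates, independent binomial outcomes and unstratified limits. The stratified figures also rest on assumed stratum sizes and rates. Nothing in the documents suggests an intention to choose the interval after seeing the results; the wording simply leaves that possible. Because the gap lies in the trial's only confirmatory decision, it should be closed before the data are final.

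**What to change.** In SAP 8.2, before database lock (the cut-off that SAP 5 already uses for settling major deviations), name one primary interval for the difference and say whether it is stratified by surgical approach.

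- **Preferred:** the Miettinen-Nurminen score interval, with power restated as about 83% at 101 per arm and about 88% at 115 per arm, for 0.95 in both arms and roughly equal arms. If it is stratified, state the assumed stratum sizes and rates as well.
- **If Wald is kept:** the 90% can stand, but state that 0.025 is nominal and that the exact one-sided error is about 3.3% at the design rates.

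Matching wording in the Protocol synopsis, 8.1 and 8.3.2 can wait for the next amendment, since Protocol 12.1 requires submission and documented approval before an amendment is implemented.

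The cost is one or two SAP sentences and, under the preferred option, a less favourable stated power. No extra patients and no change in trial conduct are requested.
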